Version 1, Version Date 06/23/2016

[figure not shown]
This draft was sent to OCCRIC on 6/24/16 as initial notification of the proposed study.

[figure not shown]
PROTOCOL SUMMARY

Title	Step-Up Intervention for Self-Management of Fatigue in Young Adults Receiving Chemotherapy
Protocol Number	
IND Sponsor	N/A
Principal Investigator /Study Chair/ Coordinating Center/Sponsor-Investigator	[name], RN, AOCN
Study Sites	Froedtert Hospital/MCW Cancer Center and Children's Hospital of Wisconsin
Clinical Trial Phase	N/A
Study Disease	N/A
Main Eligibility Criteria	1) Young adults between the ages of 18 and 39 years; 2) have a diagnosis of cancer; 3) are within the first 2 months of a chemotherapy regimen that will last at least another 3 months; 4) are ambulatory without assistance; 5) have written consent from their physician to participate; 6) have the ability to understand English; 7) have access to a computer and the Internet,
Study Rationale	Despite decades of research, fatigue remains one of the most distressing symptoms and a disabling problem for young adults with cancer. Interventions to increase physical activity have been shown to relieve fatigue in patients receiving chemotherapy, but no studies have tested a physical activity intervention to improve fatigue in young adults receiving chemotherapy. Young adults with cancer acknowledge unmet needs for information and interventions related to physical activity, and they have concerns about how and when to return to physical activity during treatment.
Primary Objectives	To determine the impact of a physical activity intervention on the self-management process variables of self-efficacy and self-regulation and their relationships to physical activity and fatigue severity.
Secondary Objectives	To determine the preliminary efficacy of a physical activity

	intervention on outcomes of physical activity and fatigue severity.
Endpoints	Self-efficacy for physical activity Self-regulation for physical activity Physical activity (steps/day) Symptom severity Fatigue severity
Study Design	A randomized experimental design with an intervention group and a usual care group
Study Agent/ Intervention Description	The physical activity intervention is based on the Individual and Family Self-Management Theory (IFSMT) and includes 3 components: 1) education about the benefits of physical activity during chemotherapy; 2) guidance and resources to help the young adult set physical activity goals during chemotherapy and to self-monitor progress toward goals with a tracking device; and 3) ongoing collaboration with a physical activity coach.
Number of Subjects	75 young adults will be recruited.
Subject Participation Duration	Patients will continue in the study for approximately 12 weeks.
Duration of Follow up	No follow-up after completion of study measures at 12 weeks
Estimated Time to Complete Enrollment:	20 months
Statistical Methodology:	Descriptive statistics will be used to describe and summarize the context variables related to the sample. Variables with significant patterns of variation will be explored as potential covariates. Field notes from sessions with the coach will be recorded and organized
Safety Assessments	The Safety Monitoring Committee of the P20 Center, the Self-Management Science Center at UWM, will be responsible for monitoring the data safety of this pilot project.
Efficacy Assessments	NA
Unique Aspects of this Study	NA

SCHEMA

Study Calendar

STUDY CALENDAR						
	Visit 1 (EN)	Visit 2	Visit 3	Visit 4	Visit 5	Visit 6
All Participants						
Medical Record Review Form	X					
Individual and Family Information Form	X					
Godin Leisure Time Index	X					
Physical Activity Assessment Inventory	X					X
Self-regulation Index for Physical Activity	X					X
PROMIS-29 (Multiple symptom severity)	X					X
PROMIS-Fatigue Short Form	X					X
Wear accelerometer (Actigraph) x 1 week	X					X
Intervention Group Participants						
The facilitator will provide initial education to participants about the benefits of physical activity, setting physical activity goals, and using a physical activity tracker (Fitbit Flex).	X					
During regularly scheduled visits for chemotherapy, the facilitator will meet with participants to deliver a 30 minute intervention: 1) review physical activity summary, 2) discuss barriers and strategies to overcome barriers, and 3) revise physical activity goals as needed.		X	X	X	X	X
Physical activity visit summary report		X	X	X	X	X
Evaluation of intervention components						X
Usual Care Group Participants						

STUDY CALENDAR						
The facilitator will provide initial education about the study and a published handout with general guidelines for physical activity during cancer treatment.	X					
During regularly scheduled visits for chemotherapy, the facilitator will meet with participants to maintain engagement in the study and identify any issues related to physical activity or participation in the study.		X	X	X	X	
Usual care visit summary report		X	X	X	X	

TABLE OF CONTENTS

Protocol Signature Page.....	2
Revision History.....	5
Protocol Summary.....	6
Schema.....	8
Study Calendar.....	10
Table of Contents.....	12
Specific Aims.....	13
Background.....	14
Study Design.....	16
Patient Selection.....	17
Study Procedures.....	17
Statistical Analysis.....	19
Adverse Events.....	20
Regulatory Compliance, Ethics, and Study Management.....	22
Data Handling and Management.....	23
References.....	25

1 SPECIFIC AIMS

Over 70,000 adolescents and young adults (AYAs) between the ages of 15 and 39 years are diagnosed with cancer each year in the United States.¹ These young patients have a unique cancer profile and frequently face months of therapy, often associated with distressing adverse side effects and decreased quality of life. Despite decades of research, fatigue remains one of the most distressing symptoms and a “major and disabling problem” for AYAs with cancer.² Persistent fatigue is implicated as one cause for the poor physical and emotional health-related quality of life outcomes in this young group of patients.³

Like many patients, AYAs receiving chemotherapy get caught in a cycle of cancer-related fatigue, which leads to decreased physical activity (PA), which contributes to deconditioning and more fatigue.⁴ An array of interventions designed to increase PA have been shown to relieve fatigue in patients with cancer receiving chemotherapy, but most of this evidence emerges from studies with middle-aged adults receiving treatment for the most common cancers. To date, no studies have tested a PA intervention to improve fatigue in AYAs receiving chemotherapy.⁵ AYAs with cancer acknowledge unmet needs for information and interventions related to PA, and AYAs report concerns about how and when to return to PA during and after treatment.⁶⁻⁹

An effective PA intervention, implemented early in the chemotherapy treatment process, is needed to prevent the cycle of fatigue and inactivity in AYAs that is associated with negative outcomes.⁴ A multi-strategy intervention that includes components of education, negotiated goal-setting, and individualized feedback, can meet this need to enable AYAs to incorporate realistic goals to stay physically active on their own. During treatment, AYAs need to adjust PA goals based on their chemotherapy administration schedules and the predictable patterns of chemotherapy-related fatigue in order to prevent weeks of decreasing activity. Most studies report that PA is safe and well-tolerated by patients receiving chemotherapy, including patients with leukemia and lymphoma, which are common cancers in AYAs.¹⁰⁻¹² Patients receiving chemotherapy can safely begin a program of low-to moderate-intensity PA on their own.¹³⁻¹⁵ Furthermore, home-based approaches may result in better maintenance of PA for AYAs with cancer who are in active treatment and who may be unwilling or unable to travel to supervised programs at alternate locations.^{6, 16, 17}

Self-management is the dynamic process by which individuals integrate strategies to manage their disease, including management of treatment-related symptoms, such as fatigue. For individuals with a chronic disease, such as cancer, this self-management process will last a lifetime, requiring the adoption of healthy lifestyle habits. The Individual and Family Self-Management Theory (IFSMT) outlines factors related to the individual's knowledge and beliefs, self-efficacy and self-regulation, which impact the self-management process to improve outcomes.¹⁸ Self-efficacy is a predictive factor for participating in PA, and promoting AYAs' self-efficacy for PA needs to be explored as a strategy to improve self-management of fatigue.¹⁹

The purpose of this research is to study a 12-week PA intervention to improve self-management of fatigue in AYAs receiving chemotherapy. The intervention will include components of education, negotiated collaboration to set individual PA goals during chemotherapy cycles, and tools for self-monitoring PA. The aims of this study are:

1. To determine the impact of the PA intervention on the self-management process variables of self-efficacy and self-regulation and their relationships to PA and fatigue severity.
2. To determine the preliminary efficacy of the PA intervention on outcomes of PA and fatigue severity.

2 BACKGROUND

Fatigue in Adolescents and Young Adults (AYAs) with Cancer

Fatigue is one of the most prevalent and severe symptoms in adolescents and young adults (AYAs) with cancer.² Defined as “a distressing, persistent, subjective sense of physical, emotional, and/or cognitive tiredness or exhaustion related to cancer or cancer treatment that is not proportional to recent activity”²⁰ (p1), cancer-related fatigue causes significant distress for AYAs and interferes with physical activities, social function, and mood.^{2, 21} AYAs commonly report that fatigue occurs with other troubling symptoms, such as poor sleep, nausea, and pain, and within these symptom clusters, fatigue is frequently named as the priority symptom.²² AYAs with cancer have shown greater symptom severity, including fatigue, than children and older patients.^{23, 24} The higher level of fatigue in AYAs may be due to their accelerated physical and cognitive growth, hormone-related changes, as well as their involvement in multiple activities of this developmental period (school, work, relationships, and parenting).³

Cancer-related fatigue is worst during the treatment period.^{2, 25} During cycles of chemotherapy, fatigue levels may follow a predictable and fluctuating pattern of increasing in the days after each cycle but improving before the next cycle.^{2, 26} Studies also show that fatigue may be a persistent long-term problem, even for AYAs who have completed treatment.^{2, 27, 28}

Physical Activity as an Evidence-based Intervention to Manage Fatigue in AYAs

Major oncology professional organizations recommend physical activity as an evidence-based intervention to manage fatigue, although most of this evidence comes from studies with adults who have the most common cancers, such as breast and prostate cancer.²⁹ Diverse PA programs for people with cancer have included aerobic and muscle-strengthening activities, such as walking, cycling, and yoga, and most programs last between 5 and 12 weeks.³⁰⁻³³

No trials have examined a PA intervention with YAs currently receiving treatment, and minimal PA studies have been conducted with patients who have the common diagnoses of this age group, such as lymphoma, leukemia, sarcoma, and germ cell tumors. A few PA interventions have targeted young adults with cancer who have completed cancer treatment, confirming that these patients are interested and able to participate in PA programs, especially when recommended by PA experts.³⁴⁻³⁶

Many young adults receiving cancer treatment unfortunately get caught in a cycle of cancer-related fatigue, which leads to decreased PA and physical fitness, which contributes to increased severity of fatigue and other symptoms.⁴ Studies confirm that PA declines in YAs during chemotherapy and persists into the years following cancer therapy.^{7, 17, 37, 38} In addition, YA cancer survivors acknowledge unmet needs for information and interventions related to PA.⁶⁻⁹ A recent analysis of topics and needs communicated by AYAs with cancer in an online forum suggests that YAs are interested in exercise for enjoyment, overall well-being, and weight management, but they do have concerns about safety and physical limitations and how/when to return to exercise post-treatment.⁹ AYAs with cancer cite barriers to PA similar to a healthy comparison group, such as lack of energy, lack of self-discipline, lack of skills, and no companions, but AYA cancer survivors may be less likely to cite ‘lack of time’ as a significant barrier.^{9, 17} An effective PA intervention, implemented early in the

chemotherapy treatment process, is needed to prevent the cycle of fatigue and inactivity in AYAs that is associated with negative outcomes.

Theoretical Framework

The Individual and Family Self-Management Theory (IFSMT) will be used as a framework for this study.¹⁸ This theory proposes three inter-related dimensions of context, process, and outcomes related to individuals' self-management behaviors. Contextual factors refer to the individual and family, the individual's health status, and the physical and social environment which influence self-management. The process dimension includes knowledge and beliefs, behavior-specific self-efficacy and self-regulation, and social facilitation. Outcome variables may be proximal, such as condition-specific self-management behaviors, and/or distal, such as quality of life or health care costs.

The IFSMT acknowledges the specific developmental and cancer-related needs of AYAs that influence their self-management behaviors. The intervention in this study (The "Step-Up" Study) contains three components

which target the self-management process:

1) education about the benefits of PA and symptom management to improve AYAs' knowledge and beliefs and self-efficacy for PA, 2) resources to increase AYAs' use of self-regulation behaviors related to PA, and 3) ongoing negotiated collaboration with a facilitator to promote PA. The impact of the intervention on the proximal outcome of engagement in PA and on the distal outcome of fatigue severity will be measured. (Figure 1).

Innovation

This study is focused on PA research with the understudied group of AYAs with cancer. It is the first study to apply the

IFSMT as a framework to identify effective interventions to help AYAs increase their PA as a strategy to manage fatigue, examining whether improved self-efficacy and self-regulation for PA as well as social facilitation will result in desired behavior changes. The intervention will be offered to AYAs who are currently receiving treatment and will be integrated into their regularly scheduled visits for chemotherapy administration, an important step to translate this evidence-based intervention into practice settings. Finally, since the intervention focuses on PA as a self-management behavior, the study will provide evidence about the impact of a less intensive and less expensive approach to improving PA, which may be a more relevant, meaningful, and feasible PA intervention for all AYAs with cancer.

Preliminary work

The multidisciplinary team comprises a unique combination of expertise in AYA oncology and PA research. [name] is an oncology nurse researcher with over 30 years of clinical oncology experience. She has conducted previous studies that described patterns of fatigue during chemotherapy cycles and the negative effects of symptoms such as fatigue and sleep-wake disturbances on the daily activities and quality of life of AYAs receiving chemotherapy.^{22, 26, 39} She has also demonstrated the feasibility and acceptability of

[figure not shown]

Figure 1. Model of PA Intervention. Adapted from *Individual and Family Self-Management Theory*, by P. A. Ryan and K. J. Sawin, retrieved from www.nursing.uwm.edu/smstc. Copyright 2009, 2014 by Ryan and Sawin. Adapted with permission.

measuring PA and symptoms in AYAs receiving chemotherapy.⁴⁰ [name] is a clinical psychologist with expertise in intervention trials related to improving PA and nutrition in cancer survivors, including adolescents. [name] has over 15 years of experience as a scientific investigator in the areas of physical activity and sedentary behavior assessment. [name] is a medical oncologist with a clinical focus on the treatment of young adult patients with sarcoma and breast cancer.

3 STUDY DESIGN

General description

The “Step-Up” Study will use a randomized experimental design to examine the preliminary efficacy of the physical activity intervention in AYAs who are receiving chemotherapy that will last approximately 12 weeks.

Number of Subjects

Seventy-five AYAs will be recruited from the Froedtert Hospital/Medical College of Wisconsin (FH/MCW) Cancer Center and Children’s Hospital of Wisconsin.

Primary Endpoints

The primary endpoints for the study include self-efficacy for physical activity, self-regulation of physical activity fatigue severity, physical activity, and fatigue severity.

The following table summarizes the proposed instruments for the study:

IFSMT factor	Variable	Measure	Pre	Post
Condition-specific: Individual	Demographics, health history, diagnosis, treatment regimen	Medical Record Review Form	x	
Condition-specific: Individual and family	Individual, household and family characteristics	Individual and Family Information Form	x	
Condition-specific: Individual	Usual amount of PA before diagnosis (self-reported)	Godin Leisure Time Index ⁴¹	x	
Process: Self efficacy	Self-efficacy for PA	Physical Activity Assessment Inventory ⁴²	x	x
Process: Goal-setting and self-monitoring	Self-regulation skills and abilities	Self-Regulation Index for PA ⁴³	x	x
Process: Negotiated collaboration	Perceptions of the intervention, preferred features of the PA tracker and facilitator	Evaluation of Intervention (intervention group only)		x
Proximal outcome: PA behaviors	# days worn, daily and weekly goals, daily step counts	PA and use of PA tracker (Fitbit) (intervention group only)	throughout	
Proximal outcome: PA behaviors	PA (steps/day)	Blinded accelerometer (ActiGraph GTx3+) x 7 days	x	x
Distal outcome: Symptom severity	Intensity of emotional distress, fatigue, pain, physical function, sleep disturbance, satisfaction with participation in social roles	PROMIS-29 ⁴⁴	x	x
Distal outcome: Fatigue severity	Fatigue frequency, duration, intensity and impact of fatigue on activities	PROMIS – Fatigue Short Form ⁴⁴	x	x

Randomization

Patients will be randomized into two groups (intervention and usual care) using the Excel 'RAND' function to create a randomization chart forcing 38 into the intervention arm and 37 into the usual care arm.

Study Timeline

Primary Completion

The study will reach primary completion 19 months from the time the study opens to accrual.

Study Completion

The study will reach study completion 22 months from the time the study opens to accrual.

4. PATIENT SELECTION

Inclusion Criteria

Patients eligible for the study will be:

- 1) between the ages of 18 and 39 years of age;¹
- 2) have a diagnosis of cancer;
- 3) are within the first two months of a chemotherapy regimen that will last at least another 3 months;
- 4) are ambulatory without assistance;
- 5) have written consent from their physician to participate;
- 6) have the ability to understand English;
- 7) have access to a computer and the Internet.

The goal of this study is to deliver the intervention as early in the treatment period as possible, but we recognize that recruiting and completing baseline measures before chemotherapy begins may be a burden to patients and a barrier to recruitment. The lower age limit for AYAs will be set at 18 years rather than 15 years in order to use one set of instruments which have been validated only for adults over age 18 years. AYAs with any diagnosis of cancer will be included in this exploratory pilot study.

Exclusion Criteria

Patients will be excluded from enrolling in the study if they have symptoms of uncontrolled cardiopulmonary disease, uncontrolled neurological disease, delayed wound healing from surgery, a high risk of bone fracture, or pre-existing peripheral neuropathy. Physicians will be asked to give written approval to indicate that patients do not have any of these contraindications to physical activity.

5. STUDY PROCEDURES

Recruitment Process

A member of the study team will screen clinic schedules at FH/MCW Cancer Center and clinic schedules in the Pediatric Hematology/Oncology Clinic to identify every AYA who meets the inclusion criteria. Clinic staff will ask eligible patients if they are willing to speak

with a member of the study team about the study. Eligible participants will be given time - over days, if necessary and possible - to consider study participation after hearing the details of the study. A member of the study team will complete the informed consent process with AYAs using an open exchange, reading through the informed consent document together, and allowing for assessment of comprehension and discussion of questions and concerns. A member of the study team will obtain written consent from the patient's primary provider to indicate the patients do not have any contraindications to physical activity.

A signed informed consent form copy will be given to the subject and a copy will be filed in the medical record. The original will be kept on file with the study records.

All patients who are consented will be registered in OnCore[®], the MCW Cancer Center Clinical Trial Management System. The system is password protected and meets HIPAA requirements.

Study Procedures

1. Visit 1 Enrollment

Following informed consent, a study team member will administer baseline surveys to all participants. Participants will receive instructions about wearing an accelerometer (Actigraph) for 1 week and how to return the accelerometer (Actigraph).

Participants will be asked for their preferred method of contact (email or phone call) to be reminded to return the accelerometer after one week of wear. A study team member will contact participants after the one-week period and remind them to return the accelerometer promptly in the mailing envelope that was provided.

Participants will be randomized to the intervention group or the usual care group.

2. Visit 2 (next regularly scheduled visit for chemotherapy)

Intervention group participants will meet with the facilitator, who will provide initial education about the benefits of physical activity and strategies to overcome barriers to physical activity, help the participants to set physical activity goals based on ability and preferences, and educate the participant on using a physical activity tracker (Fitbit Flex).

Usual care group participants will meet with the facilitator who will provide initial information to participants about the study and a published flyer about general guidelines for physical activity during treatment.

3. Visits 3, 4, 5, 6 (next regularly scheduled visits for chemotherapy – at intervals of approximately 3 weeks but may range from every 2-4 weeks based on chemotherapy schedule)

Intervention group participants will meet with the facilitator who will deliver a 30 minute intervention: 1) review physical activity summary over the past weeks, 2) identify barriers and discuss strategies to overcome barriers to physical activity, and 3) revise physical activity goals as needed. The facilitator will record physical activity data from the tracking device (Fitbit Flex), discussion notes about the barriers and strategies, and physical activity

goals. Any experiences or complications that might affect physical activity will be recorded, such as hospitalizations.

Usual care group participants will meet with the facilitator to maintain engagement in the study. The facilitator will record any experiences or complications that might be pertinent to the study, such as hospitalizations and enrollment in any activities related to physical activity.

At study visit 6, all participants will complete post-study surveys and will receive instructions about wearing an accelerometer (Actigraph) for 1 week and how to return the accelerometer (Actigraph).

A study team member will contact participants after the one-week period and remind them to return the accelerometer promptly in the mailing envelope that was provided.

Following completion of the study, a member of the study team will ensure completion and return of accelerometer (Actigraph) use by all participants. All participants will receive \$25 compensation. Intervention participants will complete an additional post-study survey to evaluate components of the intervention and be invited to keep the physical activity tracker (Fitbit Flex).

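### The Study Calendar and Section 5 disagree on whether arm-specific content precedes the baseline step count, and final steps are recorded after the fatigue score they are meant to explain

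*Combined protocol and SAP*

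**What the plan says.** **Start of arm-specific content.** In the Study Calendar, the intervention group's Visit 1 entry covers the benefits of activity, "setting physical activity goals, and using a physical activity tracker (Fitbit Flex". The usual-care entry, also at Visit 1, reads "The facilitator will provide initial education about the study and a published handout with general guidelines for physical activity during cancer treatment". The baseline accelerometer week is marked at the same visit. Section 5 places only surveys, accelerometer instructions and randomisation at Visit 1. At Visit 2 the facilitator gives the first education, sets goals and is to "educate the participant on using a physical activity tracker (Fitbit Flex"; the usual-care flyer is also handed out then.

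**Number of sessions.** The calendar marks Visits 2 to 6 for the facilitator to "deliver a 30 minute intervention: 1) review physical activity summary, 2) discuss barriers and strategies to overcome barriers". Section 5 lists that session for Visits 3 to 6 only.

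**Randomisation.** The last item under Visit 1 in Section 5 is "Participants will be randomized to the intervention group or the usual care group". It is not timed against the wear week, and nothing says when participants learn their arm.

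**Duration.** Section 1 states: "The purpose of this research is to study a 12-week PA intervention to improve self-management of fatigue in AYAs receiving chemotherapy". The Protocol Summary states: "Patients will continue in the study for approximately 12 weeks".

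**Final measures.** Section 5 states: "At study visit 6, all participants will complete post-study surveys and will receive instructions about wearing an accelerometer (Actigraph) for 1 week". Section 6, Specific Aim 1, makes accelerometer steps the second mediator and fatigue severity the outcome. Step 4 regresses fatigue on steps, controlling for self-efficacy, self-regulation and arm. Specific Aim 2 looks at baseline and post-study measures in each group and then compares groups by t-test.

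**The concern.** A baseline should be measured before the intervention can act on it. Under the calendar, an intervention participant has goals and a tracker when the baseline week begins. Any early rise in steps is then subtracted from the later change, so a real benefit would probably look smaller. Steps/day is among the endpoints that Section 3 lists as primary.

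A mediator should be measured before the outcome it is said to influence. Here the fatigue score comes first and the steps follow. Section 1 describes a cycle in which fatigue lowers activity and lower activity adds to fatigue. A tired participant who walks less in the following week produces the association Step 4 looks for, even if activity has no effect on fatigue. A significant Step 4 and Sobel test could then be taken as support for activity relieving fatigue.

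**Working it through.** **1. Is the calendar entry one misplaced mark?** No. The calendar has five 30-minute sessions (Visits 2–6) and Section 5 has four (Visits 3–6). The calendar's Visit 2 session already reviews an activity summary, which fits a tracker issued at Visit 1.

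**2. Does the stated duration settle which version governs?** Visits are about 3 weeks apart (range 2–4).
- Visits 2–6: 4 gaps × 3 = 12 weeks (8–16). This fits a 12-week intervention starting at Visit 2.
- Visits 1–6: 5 gaps × 3 = 15 weeks (10–20), if the first gap is like the others. The Protocol Summary puts all participation at about 12 weeks.

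The evidence is mixed, and the ranges are wide enough that neither version is excluded.

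**3. Effect on the steps comparison if the calendar is followed.** The plan gives no figure for this point. Its analysed sample of 68 is used as an input. For a four-predictor model at alpha 0.10, with f² = 0.15 assumed for a medium effect, the noncentral F calculation needs 69, and 68 gives 79.6% power, so the stated number reproduces.

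Assumed inputs: d = 0.5 on steps, baseline-to-final correlation ρ = 0.5, two-sided alpha 0.10 (the plan does not state sidedness), and a share q of the between-arm effect already present in the baseline week.
- Change score: effect = d(1 − q)/√(2(1 − ρ)). With ρ = 0.5 the divisor is 1.
- Baseline-adjusted: effect = d(1 − ρq)/√(1 − ρ²).
- Noncentrality = effect × √(34/2) = effect × 4.12, with 66 df (one fewer for the adjusted analysis, ignored here).

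| q | Change-score effect | Power, change score | Power, baseline-adjusted | Power, final steps only |
|---|---|---|---|---|
| 0 | 0.500 | 65% | 76% | 65% |
| 0.25 | 0.375 | 46% | 66% | 65% |
| 0.50 | 0.250 | 27% | 55% | 65% |
| 0.75 | 0.125 | 14% | 43% | 65% |

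Over the same q values, change-score power is 53%, 36%, 22%, 13% at ρ = 0.3 and 84%, 63%, 37%, 17% at ρ = 0.7. With ρ = 0.5, going from q = 0 to q = 0.5 lowers it from 34% to 16% at d = 0.3 and from 95% to 50% at d = 0.8. The relevant q is the net difference between arms, because the usual-care handout also moves to Visit 1.

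**4. Step 4 when activity has no effect on fatigue.** Simulated trials, N = 68, alpha 0.10. Assumed: each main mediator shifted by 0.5 SD, paths of 0.3 from each to steps, correlation 0.5 between baseline fatigue and fatigue at the start of the wear week, 0.7 between the start and end of that week, and 1 SD more fatigue lowering steps by 0.2 to 0.36 SD.

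- Post-study fatigue as outcome, schedule as written: Step 4 is significant in 49% to 91% of trials if start-of-week fatigue drives steps, and in 43% to 86% if fatigue throughout the week does.
- Change in fatigue as outcome, same schedule: about 17% to 38% across the two drivers. With a baseline correlation of 0.5, the change correlates with the post score at √((1 − 0.5)/2) = 0.5, so the association is halved, not removed.
- No reverse effect: close to the nominal 10%.
- Wear week moved before the fatigue score, post-study outcome: 30% to 66% (start-of-week driver) and 43% to 86% (whole-week driver, no gain). Adding baseline fatigue to the moved schedule gives 23% to 50% and 36% to 78%.

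**5. The whole step sequence.** As scheduled with the post score, Steps 1–4 all pass in 3% to 7% of trials when the intervention does not change fatigue (0.7% without a reverse effect). If the intervention lowers fatigue by an assumed 0.5 SD through some other route, they pass in 21% to 44% (5% without a reverse effect).

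**The case against.** Section 5 is the detailed procedure, and under it the baseline week is sound provided Visit 2 falls at least 7 days after Visit 1. That stands. A reader might infer that both wear weeks are misplaced, but the documents show this only for the final one. At baseline they show a conflict, plus an unstated minimum gap and disclosure time.

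Specific Aim 1 does not say whether fatigue enters as the post score or as a change. Reading it as a model with no earlier fatigue value treats silence as fact, and the highest Step 4 rates depend on that reading. This also stands, although the rate exceeds 10% under either reading.

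A reader might also infer that false mediation claims would be frequent. The joint rate of 3% to 7% does not support this when the intervention leaves fatigue unchanged. The 21% to 44% needs a fatigue benefit by another route, which is an assumption. Section 4 calls the study an exploratory pilot, so the second part mainly limits interpretation. It still matters, because these relationships belong to the primary objective and the sample size was built on the mediation model.

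Finally, surveys precede wear at both time points. Moving only the final wear week would break that symmetry, and it gives no gain if fatigue throughout the week drives steps. The objection to treating the move as necessary therefore holds.

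**Conclusion.** Two facts rest on the text alone. The calendar and Section 5 disagree on the visit at which arm-specific content starts and on the number of sessions. The Visit 6 fatigue score precedes the steps that Step 4 uses to explain it.

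The baseline harm is conditional: the calendar must be followed and the Aim 2 t-tests must use change from baseline, which Section 6 does not settle. In that case power could fall from 65% to between 46% and 14%. A t-test on final steps alone is unaffected. The second part holds under both schedules: Step 4 and the Sobel test do not establish direction. Every percentage depends on assumed effect sizes, correlations and reverse effects; none comes from the documents. The point should be fixed before enrolment, since wear-week timing cannot be corrected afterwards.

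**What to change.** - **Schedule.** Reconcile the Study Calendar with Section 5 on the visit at which arm-specific content starts and on the number of sessions. Whichever version is kept, complete the baseline wear week before that content and before allocation is disclosed, and say so.
- **Specific Aim 2.** Compare final steps between arms adjusted for baseline steps. In the table this clearly beats final steps alone only when the baseline week is clean (76% against 65%).
- **Specific Aim 1.** Use post-study fatigue as the outcome, with baseline fatigue as a covariate in Steps 1, 4 and 5. This does not remove reverse causation, so report Step 4 and the Sobel test as associations whose direction is not established.
- **Optional.** Wear the final device before Visit 6. This helps only partly, and not at all if fatigue throughout the week drives steps. If adopted, match it at baseline. The documents give no recall period for the fatigue forms, so strict ordering could not be confirmed even then.

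**Cost.** A small amendment and calendar correction, with the same devices and questionnaires. If randomisation waits for the wear week, a few participants may be lost before it. If the calendar version is kept, an additional contact before the arm-specific content may be needed, and Section 4 already names baseline burden as a barrier to recruitment.
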